5.1.1 Missing data

The primary outcome is based on hospital records of date of admission and date of discharge and will have no missing data. Similarly, the baseline variables included in the adjusted model should not have any missing data, perhaps with the exception of the number of admissions and numbers of bed-days in the previous 2 years if the patient has recently moved to the Trondheim region. If this occurs, we anticipate that very few participants will have missing information for these variables. The need to employ missing data strategies, such as multiple imputations, will be considered depending on the proportion of missing information.

5.1.2 Subgroup analyses and treatment effect heterogeneity

To assess for treatment effect heterogeneity, subgroup analyses will be performed based on the covariates listed above (§5.1). For continuous covariates (age, number of previous admissions and duration of previous admissions), we will assess the appropriateness of including these in the mixed linear regression model with an interaction term for investigating treatment effect heterogeneity.

5.1.3 Additional analyses

The primary analysis and subgroup analyses will also be performed on the per protocol population.

STATISTICAL ANALYSIS PLAN for BAB-study

5.2 Analysis of secondary outcomes

Table 1: Overview of secondary outcomes and their planned analyses

Secondary outcomes	Time(s) recorded	Timepoint / timeframe for analysis	Planned analysis	Brief description of recorded data
Clinical assessments and treatment during admission				
Sleep wake cycle parameters	Daily	During admission	Linear	Algorithm estimated variables (from Xenthrum radar sensors)
Clinical Global Impression Scale – Improvement (iCGI-I) - During admission (day-to-day change) - Change from admission	Daily Discharge	During admission At discharge	Linear Linear	Range: -6 (maximum deterioration) to 6 (ideal improvement)
Clinical Global Impression – Severity sub scale (CGI-S)	Baseline and discharge	At discharge	Linear	Likert scale with range: 1 (Normal, not at all ill) to 7 (Among the most extremely ill patients)
Suicide risk	Daily	During admission	Logistic	One item clinical assessment
Need for continuous observation (due to suicide risk)	Daily	During admission	Logistic	One item clinical assessment
Risk of harm to others (Brøset Violence Checklist)	8-hrly	During admission	Linear	6 item scale assessing 6 observable behaviours scored on binary scale. Risk of violence based on total scores: low = 0; moderate = 1-2, higher >2
Staff Observation Aggression Scale-Revised (SOAS-R)	Daily	During admission	Linear	Context and severity of aggressive incidents recorded on scale with range 0 to 100 (0 = not severe, 100 = very severe)
Medication use	Daily	During admission	Logistic/Linear ^a	Daily doses and classes of medication recorded
Change in admission status	Daily	During admission	Logistic ^b	Changes from involuntary to voluntary and vice versa will be recorded
Patient-related experiences and other outcomes				
Adherence (item checklist)	Daily	During admission	Logistic	Duration and reason for exposure to normal lighting; use of blue-blocking glasses on exiting unit and filters on media devices
Satisfaction and benefits	Discharge	At discharge	Linear	10 items scored on 5-point Likert scale (1 = low satisfaction)

^aWe will first consider use of anxiolytic and hypnotic medication in addition to the frequency of extra medication that is taken as required (pro re nata). The dosage, frequency and changes in the use of different medication classes will be considered in exploratory analyses later; ^bChange in admission status will be investigated both as the proportion of involuntarily admitted patients who change to voluntary admission, and the number of days of involuntary admission.

STATISTICAL ANALYSIS PLAN for BAB-study

5.2.1 Analysis of continuous secondary outcomes

For continuous variables measured only at discharge (iCGI-I and measure of satisfaction), between group comparisons will be conducted using linear regression adjusting for the same covariates as the in the primary analysis.

The remaining continuous variables are measured two or more times per admission, and these will be analysed using a mixed linear regression model. Where possible, we will use a three-level linear mixed-model with respective secondary outcome as the dependent variable, timepoint (or day of admission) as level 1, admissions within patient as level 2, and patient as level 3. The covariates will include treatment allocation, the prespecified baseline variables and an interaction term between treatment and day of admission. If the model fails to converge, we will consider removing the interaction term and or reduce the number of levels.

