3.1 Confidence intervals and p-values

All efficacy and safety estimates will be presented with two-sided 95 % confidence intervals. Accompanying two-sided p-values will be calculated and compared to a 5 % significance level. No adjustments for multiplicity will be made since there is only one primary null hypothesis in this trial. This is in line with “Guideline on multiplicity issues in clinical trials EMA/CHMP/44762/2017”.

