5.1 Analysis of primary outcome

The primary outcome is duration of admission in days in the ITT population. Some patients will be readmitted and re-randomized during the study period. As such, we plan to use a two-level linear mixed-model with duration of stay as dependent variable, with admissions within patient as level 1, and patient as level 2. The primary covariate is group (blue-depleted evening lighting versus normal lighting condition). We will adjust the analyses for a set of pre-specified baseline variables which can be strong predictors of the outcome, as generally recommended by Kahan et al³ and Vittinghoff et al⁴.

These covariates are:

- Age
- Sex
- Diagnosis (categorized as psychotic episodes/disorders, manic episode, severe depressive episode, or none of these)
- Comorbidities (categorized as alcohol/substance use disorders, borderline or other personality disorders, or none of these two)
- Involuntary versus voluntary status at admission
- Number of admissions in the previous 2 years
- Number bed-days in the previous 2 years.

If the model fails to converge using a two-level model we will consider a single-level model.

As this primary outcome is heavily skewed and not normally distributed, we anticipate the use of bootstrapping with the bias-corrected and accelerated (BC_a) method and B=5000 bootstrap samples. If this results in unpractical long computing time, we will use a lower number of bootstrap samples, such as B=1000.

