5.2.2 Analysis of binary secondary outcomes

Binary secondary outcomes recorded on a daily basis will be analysed using a three-level mixed logistic regression model with the same levels and covariates as described in the mixed linear models above (§5.2.1). Depending on the convergence of the model and frequency of the outcomes, these variables may be simplified into a single binary variable across the entire admission (for example, a binary variables representing suicide risk any time during the admission).

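### The repeated-measures models name levels but no random slope or serial correlation, so the treatment-by-day test on daily and 8-hourly secondary outcomes may not keep its 5% level

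*SAP*

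**What the plan says.** SAP 5.2.1 covers continuous outcomes measured two or more times per admission. Where possible they get a three-level linear mixed model with "timepoint (or day of admission) as level 1, admissions within patient as level 2, and patient as level 3". The covariates are treatment, the pre-specified baseline variables and "an interaction term between treatment and day of admission". The fallback reads "If the model fails to converge, we will consider removing the interaction term and or reduce the number of levels".

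SAP 5.2.2 gives daily binary outcomes a "three-level mixed logistic regression model with the same levels and covariates as described in the mixed linear models above", with the option of collapsing them to one value per admission.

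On inference, SAP 3.1 states "Accompanying two-sided p-values will be calculated and compared to a 5 % significance level", and "No adjustments for multiplicity will be made since there is only one primary null hypothesis in this trial".

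Table 1 in SAP 5.2 lists most of the repeated outcomes as daily and the Brøset checklist as 8-hourly, analysed linearly. No random slope, residual correlation structure or robust standard error is named for any of them. The bootstrap in 5.1 is planned for the primary outcome only.

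**The concern.** Levels without slopes are conventionally random intercepts. Such a model assumes that, apart from its starting level, every admission follows the mean course of its arm, and that readings are otherwise independent. Neither is likely in a trans-diagnostic acute ward with readings every day or every 8 hours.

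When an admission has its own rate of change, the model treats that departure as independent noise spread over many readings. A long stay then counts as plentiful evidence on the slope, although it is one trajectory. Unequal stays make this worse, and SAP 5.1 says of length of stay: "As this primary outcome is heavily skewed and not normally distributed".

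At stake is the time-course comparison for the daily and 8-hourly secondary outcomes. Each is read at an unadjusted 5%, so a difference in trajectory between lighting groups could be reported when there is none.

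**Working it through.** **Inputs from the SAP.** Two-sided 5% level (3.1); three levels and treatment-by-day (5.2.1); daily and 8-hourly readings (Table 1); skewed stays (5.1); 1:1 allocation (2.2).

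**Assumptions, because the SAP gives no figure.** Random-intercept SD and residual SD both 1; slope SD τ of 0.03 to 0.2 residual SD per day; first-order autocorrelation 0.3 to 0.7; 200 or 400 admissions, one per patient; stays either fixed at 4, 7 or 14 days, or log-normal with median 6 days, log-SD 0.9 and a cap. A day main effect was fitted alongside the interaction. The true treatment effect is zero, so every rejection at |z| > 1.96 is a false positive. There were 500 runs per setting unless stated.

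**Step 1: reproduce the stated 5%.** When the truth is intercepts only, treatment-by-day is rejected in 3.4% to 6.0% of runs. The plan's level holds under its own assumption.

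**Step 2: fixed stays, closed form.** With T readings per admission and Sxx the sum of squared deviations of time (in days), the slope from one admission has variance 1/Sxx + τ². The intercepts-only model folds the slope variation into the residual and uses 1/Sxx + τ²/(T−1). Hence

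true SE / model SE = R = √[(1/Sxx + τ²) / (1/Sxx + τ²/(T−1))], and the false-positive rate is 2[1 − Φ(1.96/R)].

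The number of admissions cancels. With τ = 0.1:

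- 7 days, daily: T = 7, Sxx = 28. R = √(0.0457/0.0374) = 1.11, giving 7.6%.
- 14 days, daily: T = 14, Sxx = 227.5. R = √(0.0144/0.00516) = 1.67, giving 24%.
- 14 days, 8-hourly: T = 42, Sxx = 685.6. R = √(0.01146/0.00170) = 2.59, giving 45%.

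Simulation agrees. For τ = 0.05/0.1/0.2 a fixed 7-day stay gives 5%/8%/15% daily and 7%/12%/30% 8-hourly. A fixed 14-day stay gives 12% to 43% daily and 23% to 61% 8-hourly. A fixed 4-day stay with daily readings gives only 5% to 8%.

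**Step 3: skewed stays, 400 admissions.** False positives for treatment-by-day:

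| Truth | Daily | 8-hourly |
|---|---|---|
| Linear slopes, stays to 60 days, τ = 0.03/0.05/0.1/0.2 | 50%/62%/82%/89% | 65% to 91% |
| Linear slopes, stays capped at 21 days, τ = 0.05/0.1 | 25%/43% | 36%/61% |
| Linear slopes, stays capped at 14 days, τ = 0.05/0.1 | 12%/24% | 19%/44% |
| Plateau (time constant 7 days, amplitude SD 0.5 to 1), caps of 14 to 60 days | 8% to 23% | 12% to 39% |
| No slope variation, autocorrelation 0.3/0.5/0.7 | 13%/25%/41% | 16%/27%/37% |

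The caps are modelling assumptions and are unrelated to the data cut-off in SAP 2.6.

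**Step 4: other contrasts.** With the interaction removed, the treatment effect is rejected in 3% to 7% of runs in every setting. With the interaction kept, the treatment effect at day 0 reaches 27% under linear slopes over stays to 60 days. It is about 3% to 8% once trajectories level off, slopes shrink with longer stay, or only autocorrelation is present.

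**Step 5: does the remedy work?** With 200 admissions, skewed stays, daily readings and 120 runs (Monte Carlo error about 2 points):

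| Truth | Intercepts only | Random slope for day added |
|---|---|---|
| τ = 0.1 | 78% | 5.0% |
| Autocorrelation 0.5 | 24% | 3.3% |
| Both | 80% | 6.7% |

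Some fits gave convergence warnings. Cluster-robust standard errors on the intercepts-only fit gave about 3% to 6% with fixed stays but about 5% to 17% with skewed stays. Restricted to a 7–14 day window they gave 5% to 6%.

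**The case against.** **The SAP never says intercepts only.** True: this is an inference from a model described by levels. SAP 3.4.2 also provides for assumption checks and a published amendment before unblinding. But it names no check of slopes or serial correlation, and the only changes 5.2.1 describes make the model simpler. The inference is the natural one.

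**The large figures come from the tails.** A reader might infer that most time-course tests would be false positives. The documents do not support that: the rates above 50% need each patient to drift linearly through a long stay, with a slope unrelated to its length. Several scales are bounded, such as the six binary Brøset items. With τ = 0.03/0.05/0.1 and daily readings, letting change stop after day 7 gives 7%/7%/10%, stopping after day 14 gives 8%/21%/35%, and letting slopes shrink as stays lengthen gives 5%/9%/16%. This objection stands on size. It does not remove the inflation, and autocorrelation alone produces it without any slope variation.

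**The interaction is not designated as the test.** Also true. 5.2.1 lists it among the covariates, and 5.2.3 speaks only of an effect of the lighting conditions. That leaves the reported contrast open, which is part of the problem.

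**Not every outcome is touched alike.** Daily iCGI-I is a day-to-day change score, so differing recovery rates do not carry over to it directly.

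**Conclusion.** The point holds in conditional form. Followed as written, the model in 5.2.1 gives too small a standard error for treatment-by-day whenever trajectories differ between admissions or neighbouring readings correlate, both likely with these data.

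The size depends on slope variance, autocorrelation and length of stay, none of which the SAP gives. It is close to the nominal 5% with short, equal stays and weak slope variation. It is roughly 8–45% with stays capped at 14 days, plateauing trajectories or autocorrelation of 0.3–0.7, and above 50% only under linear change sustained through long stays.

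One might also infer that the treatment effect in general is mis-tested. It is not: averaged over the stay it keeps about 5%, and the day-0 effect is clearly inflated only in the linear, long-stay case. CGI-S (baseline and discharge only), outcomes collapsed to one value per admission, and the primary outcome are unaffected. The logistic models in 5.2.2 share the structure, but no size is claimed for them. Because only secondary outcomes are involved, this should be fixed but does not threaten the trial's main conclusion.

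**What to change.** - **5.2.1:** add a random slope for day at admission level, correlated with the random intercept. Add first-order autoregressive residuals for the 8-hourly scores.
- **5.2.2:** add the random slope where event frequency allows.
- **Both:** state which treatment contrast is reported for each outcome, either treatment-by-day or the effect averaged over the stay.
- **Fallback:** if the slope model does not converge, do not test treatment-by-day from an intercepts-only fit. Either drop the interaction and report the average treatment effect, or restrict the analysis to a fixed early window with patient-clustered robust standard errors. Robust errors over the whole of skewed stays are not sufficient.

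The cost is a few sentences, longer fitting, wider intervals for time-course effects and some added convergence risk, greatest for the three-level logistic models. The change can be made as an SAP amendment before unblinding, the route 3.4.2 already provides.

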3.4.2 Blinded statistician

The analyses will be performed by the trial statistician who will be masked to the lighting conditions experienced by each group for the primary analysis and as far as practically possible for subsequent analyses. This document details the analyses planned *a priori* along with the anticipated assumption checks of the chosen analysis models. These model assumption checks and decisions about the final model will be performed prior to unblinding of the statistician and, if necessary, detailed in an amendment to the SAP that will be published together with the trial results.

4. Presentation of study population

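### CGI-S is to be compared at discharge, but the mixed model it is sent to defines no discharge contrast and does not adjust for baseline CGI-S

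*SAP*

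**What the plan says.** In Table 1 (SAP section 5.2) the CGI-S row gives the recording times as "Baseline and discharge", the analysis timepoint as discharge, and the method as linear.

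Section 5.2.1 divides the continuous outcomes in two. Ordinary linear regression applies to those it introduces as "For continuous variables measured only at discharge (iCGI-I and measure of satisfaction", and CGI-S is not among them. For the rest, "The remaining continuous variables are measured two or more times per admission, and these will be analysed using a mixed linear regression model". CGI-S has two measurements per admission, so it falls under this second rule.

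The levels of that model are "timepoint (or day of admission) as level 1, admissions within patient as level 2, and patient as level 3". Its fixed effects are described in one sentence: "The covariates will include treatment allocation, the prespecified baseline variables and an interaction term between treatment and day of admission". If the model does not converge, the interaction may be dropped or the number of levels reduced.

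The baseline variables are those of section 5.1, where "We will adjust the analyses for a set of pre-specified baseline variables which can be strong predictors of the outcome". They are age, sex, diagnosis, comorbidities, admission status, and admissions and bed-days in the previous two years. Baseline CGI-S is not one of them.

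**The concern.** Table 1 promises a comparison of severity at discharge. Section 5.2.1 sends that comparison to a model whose only named time term is treatment by day of admission, and it does not say which coefficient or contrast is the discharge difference. For CGI-S, day is a poor time axis: there are only two values per admission, and the day of the second is the length of stay, which is the primary outcome.

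Discharge severity matters for reading the primary result. If stays are shorter under blue-depleted light, the reader will ask whether those patients left equally well or in a worse state. With numeric day, the same improvement reached in fewer days appears as a steeper slope, so a shorter stay can look like a CGI-S benefit when discharge severity is the same in both arms.

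Separately, even a sound baseline/discharge coding with the listed free treatment main effect gives a discharge contrast unadjusted for baseline CGI-S, although that value is collected.

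**Working it through.** The SAP gives no CGI-S figure to reproduce, so this sets out what each coding estimates and then sizes the difference under assumed inputs.

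**1. Numeric day.** With T for treatment, a day main effect included, and day = 0 at baseline and D at discharge:

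E(Y) = b0 + b1·T + b2·day + b3·T·day

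The arm difference at day d is b1 + b3·d. So b1 is the day-0 difference and b3 a slope per day. The difference in mean discharge severity is

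b1 + b3·E(D|T=1) + b2·[E(D|T=1) - E(D|T=0)]

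No single coefficient equals this, and the last term carries the effect on length of stay. For the direction, take a fall of 1.0 in both arms and stays of 6 and 4.8 days (20% shorter). The slopes are -1/6 = -0.167 and -1/4.8 = -0.208 per day, a gap of -0.042 with no difference at discharge. Fitted gaps are smaller when stays vary (step 5).

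**2. Baseline/discharge indicator V (0, 1).**

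E(Y) = b0 + b1·T + b2·V + b3·T·V

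The discharge difference is b1 + b3. If the interaction is dropped, as the convergence rule allows, b1 averages the two times: for a true difference of -0.30 it becomes (0 - 0.30)/2 = -0.15.

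**3. Precision by hand.** Assume 200 single admissions per arm, SD 1 and correlation 0.4. The unadjusted contrast has SE = sqrt(1/200 + 1/200) = 0.100. Adjusting for baseline gives 0.100 × sqrt(1 - 0.4²) = 0.092.

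**4. Simulation inputs, all assumed.** 400 admissions in about 290 patients; baseline CGI-S 5.0, SD 1; within-admission correlation 0.2-0.6, half of it shared across a patient's admissions; lognormal stay with median 6 days and sigma 0.7-1.0; stays equal or 20% shorter under treatment; 1,000 replicates per scenario; REML fits with Wald tests. Numeric-day fits include a day main effect.

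**5. Simulation results.**

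*True discharge difference -0.30, fall of 1.0 unrelated to stay:*
- Numeric day: treatment coefficient -0.06 to -0.11, interaction -0.008 to -0.043 per day. With equal stays the implied difference runs from -0.08 to -0.12 at day 1 to -0.35 to -0.72 at day 30.
- The other three models all give about -0.30. At correlation 0.4:

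| Model | SE | Power |
|---|---|---|
| Indicator, free treatment main effect | 0.098 | 85-89% |
| Indicator, baseline means constrained equal | 0.091 | 90-93% |
| Discharge regressed on treatment and baseline | 0.091 | 89-93% |

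The power gain over the free indicator is 0-3 points at correlation 0.2 and 9-10 points at 0.6.

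*No CGI-S effect, correlation 0.4, rejection at nominal 5%:*
- Numeric-day interaction: 15-32% (fall of 1.0 unrelated to stay; 8-45% for falls of 0.5-1.5), 8-46% (half the fall grows with log stay), 4-6% (fall proportional to stay). With stays 20% shorter and a fall of 1.0 unrelated to stay, it averages -0.008 to -0.016 per day and rejects in 32%.
- Baseline-adjusted regression: 4-7% throughout.
- Indicator models: 4-6%, except 6-13% when the fall is proportional to stay, because they assume equal variance at both times.

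*About 28% of discharge values missing, dependent on baseline:* baseline-adjusted -0.31 (SE 0.111, power 79%), constrained indicator -0.31 (0.107, 82%), free indicator -0.30 (0.114, 75%); error rates 4-5%.

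**6. Different assumptions.** A smaller simulation (40 replicates; 400 single admissions, mean stay about 10 days, fall 1.5, between-patient and residual SD 0.7 each, true difference -0.5) gave -0.49 with the indicator and -0.50 with baseline adjustment. Numeric day gave -0.17 for treatment and -0.32 at day 10. The indicator model without interaction gave -0.24. Fitting only the listed terms, without a day main effect, made the interaction significant in all 40 replicates under no effect, because it absorbs the general improvement over time.

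**The case against.** The strongest reply is that the SAP nearly settles the coding. Level 1 may be a timepoint rather than a day, CGI-S has two named timepoints, and Table 1 fixes the comparison at discharge. On that reading, day of admission in the interaction is shorthand for the level-1 term. The list of covariates need not be exhaustive, and section 3.4.2 says "These model assumption checks and decisions about the final model will be performed prior to unblinding of the statistician". The result would then be unbiased and the loss only precision. This is a fair reading, and it limits the size of the point. But the SAP makes no choice for CGI-S, and it writes the interaction only with day. Section 3.4.2 is a route for repair, not a definition of the contrast.

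The error rates under numeric day also depend on assumptions the SAP cannot settle, from 4-6% to 46%. Nor are they all due to shorter stays. With single admissions, correlation 0.4 and a fall of 1.0 unrelated to stay, the interaction rejected in 14% (sigma 0.7) and 27% (sigma 1.0) with equal stays, against 34% and 33% with stays 20% shorter. At sigma 1.0 most of the excess comes from forcing a straight line in day on skewed stays. That objection stands: 32% is not the effect of a shorter stay. What a shorter stay adds is the shift in one direction.

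The 5.1 covariates were not simulated and could already take up part of what baseline CGI-S explains, so the precision gain may be overstated. CGI-S was simulated as continuous and unbounded, although it is a 1-7 scale.

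Finally, section 5.2.3 reserves multiple imputation for outcomes that mixed models cannot handle. It fits once discharge CGI-S is treated as a single measurement with baseline as a covariate, but imputation itself was not simulated, and with missing data the constrained indicator model was slightly more precise.

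**Conclusion.** The point holds and should be corrected before unblinding; confidence is medium. The SAP names discharge as the timepoint for CGI-S but does not define the contrast in the model it assigns, and the one time term it names does not give that contrast if day is numeric.

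Under numeric day and the assumed inputs, a true difference of -0.30 appears as a treatment coefficient of -0.06 to -0.11, and false positives on the interaction range from 4-6% to 46% according to how improvement relates to stay. Under the permitted baseline/discharge coding there is no bias in the estimate, and the cost is about 7% in standard error at correlation 0.4 (0.098/0.091 = 1.08). One secondary outcome is affected and the primary analysis is untouched.

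**What to change.** State in section 5.2.1 that discharge CGI-S will be regressed on treatment, baseline CGI-S and the section 5.1 covariates, with a random intercept for patient, since "Some patients will be readmitted and re-randomized during the study period". Add that missing discharge values follow the multiple imputation rule of section 5.2.3.

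A mixed model with a baseline/discharge indicator is a close alternative if baseline means are constrained equal across arms and the two times have separate variances. With a free treatment main effect it gives the less precise, unadjusted contrast.

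A minor companion change: list day of admission as a fixed main effect in 5.2.1, and so in 5.2.2, and keep it if the interaction is dropped. This matters only if the listed terms would be fitted literally.

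The main change is two sentences, made through the pre-unblinding amendment that section 3.4.2 provides for. No new data are needed, because baseline CGI-S is already recorded.

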1.2 Background and rationale for the trial

There is increasing recognition of the need to stabilize sleep-wake cycles in individuals with major mental disorders. As such, clinicians and researchers advocate for the use of interventions targeted at sleep and circadian dysrhythmias as an adjunct to the standard treatments offered for acute illness episodes of a broad range of diagnoses. This project explored the benefits of admitting individuals with major mental disorders to an acute psychiatric inpatient unit where changes in light exposure are integrated into the therapeutic environment of a new psychiatric unit.

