2.7 Data sources and timing of endpoint assessments

The primary outcome is duration of admission which is assessed upon discharge. Other secondary and exploratory outcomes are assessed either daily or upon discharge (See Table 1 in the published protocol¹). Data will be obtained from two main sources: Electronic patient records and Xethru radar sensors as described in the published protocol.

The Xethru radar sensors will be used to obtain data on each patient's sleep-wake cycle. As described in the published protocol, developed algorithms will be used to estimate the total sleep time (TST), sleep onset latency (SOL), number of nocturnal awakenings (NW), wake after sleep onset (WASO), and sleep efficiency (SE%)².

STATISTICAL ANALYSIS PLAN for BAB-study

3. Statistical principles

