4.2 Baseline patient characteristics

As described in the protocol, the following participant demographics and baseline characteristics to be summarised include:

- Demographics: Age, sex, ethnicity, marital status, living situation, years of education, employment status
- Current diagnosis or diagnoses, according to International Classification of Disease 10 (ICD 10) at discharge
- Type of admission (voluntary or involuntary)
- Previous admission history: number of admissions, total number of inpatients bed-days in the 2 years prior
- Details of current presentation based on health records: sleep problems during previous month, level of functioning, alcohol and substance misuse, risk of or actual harm to self or others, current physical health
- Past psychiatric and forensic history, and history of comorbid illnesses

These demographics and baseline characteristics will be tabulated for each treatment arm and overall using descriptive statistics:

- Continuous variables: N, mean and standard deviation, and median and 25th and 75th percentiles as appropriate
- Categorical variables: counts and percentages for categorical variables.

No formal statistical comparisons of baseline characteristics will be conducted.

STATISTICAL ANALYSIS PLAN for BAB-study

5. Analysis

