5.4 Analysis of exploratory outcomes

Planned exploratory analyses to be assessed in subsequent papers include:

- Causal mediation analyses to determine if improvement in sleep variables and intra-individual variability in sleep variables mediate the effect of the blue-depleted lighting conditions on duration of admission and risk of harm to self or others
- The dosage, frequency and changes in the use of different medication classes will be considered in exploratory analyses later

6. Reference

1. Scott J, et al. A pragmatic effectiveness randomized controlled trial of the duration of psychiatric hospitalization in a trans-diagnostic sample of patients with acute mental illness admitted to a ward with either blue-depleted evening lighting or normal lighting conditions. *Trials* 2019; **20**(1): 472.
2. Heglum HSA, et al. Distinguishing sleep from wake with a radar sensor A contact-free real-time sleep monitor. *Sleep* 2021; **44**(8): zsab060.
3. Kahan BC, et al. The risks and rewards of covariate adjustment in randomized trials: an assessment of 12 outcomes from 8 studies. *Trials* 2014; **15**: 139.
4. Vittinghoff E, et al. Regression methods in biostatistics linear, logistic, survival, and repeated measures models. 2nd ed. New York: Springer; 2012.
5. Viola AU, et al. Blue-enriched white light in the workplace improves self-reported alertness, performance and sleep quality. *Scand J Work Environ Health* 2008; **34**(4): 297-306.

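### Prior-month sleep problems are recorded but left out of the radar sleep-outcome models; adding them is a nearly free, modest gain in precision

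*SAP*

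**What the plan says.** Section 2.7 names the source of the sleep outcomes: "The Xethru radar sensors will be used to obtain data on each patient's sleep-wake cycle". Algorithms turn the signal into five variables: total sleep time, sleep onset latency, number of awakenings, wake after sleep onset and sleep efficiency. Table 1 in section 5.2 lists them as recorded daily during admission and analysed by linear models.

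Section 5.2.1 gives the model for outcomes measured more than once per admission: "The covariates will include treatment allocation, the prespecified baseline variables and an interaction term between treatment and day of admission". The baseline set comes from section 5.1, which gives the reason for choosing it: "We will adjust the analyses for a set of pre-specified baseline variables which can be strong predictors of the outcome". The outcome there is length of stay. The set is age, sex, diagnosis, comorbidities, legal status at admission, and admissions and bed-days in the previous two years.

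Section 4.2 includes among the characteristics to be summarised: "Details of current presentation based on health records: sleep problems during previous month". The only use it states is descriptive: "These demographics and baseline characteristics will be tabulated for each treatment arm and overall using descriptive statistics".

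**The concern.** Section 5.1 justifies adjustment by prognostic strength for the outcome being analysed. Section 5.2.1 carries the resulting list over to sleep outcomes, where that reasoning was not applied again. A patient's recent sleep is an obvious candidate predictor of sleep on the ward, and the SAP already plans to have a record of it. The trial's rationale in section 1.2 concerns "interventions targeted at sleep and circadian dysrhythmias", so the sleep outcomes are not peripheral.

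Two things are at stake. Intervals for the five sleep contrasts may be somewhat wider than they need be, and a chance difference between arms in prior sleep stays uncorrected. If the item is added only after allocation is revealed, the adjustment will look data-driven.

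**Working it through.** **Is a better baseline available?** Section 2.2 places randomisation before arrival at the unit. Section 2.7 and Table 1 place radar recording during admission. It follows, although the SAP does not say so outright, that no radar value precedes allocation. CGI-S, by contrast, has a baseline entry in Table 1. The health-record item in section 4.2 is the only measure of sleep before admission that the SAP names.

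**How much could it explain?** The SAP states no sample size, SD, prevalence or correlation, so there is no figure of its own to reproduce. The inputs below are assumptions:
- p, the share of admissions with a recorded sleep problem: 0.4, 0.5 or 0.7.
- d, the gap in admission-level sleep between those with and without a problem, in within-group SD: 0.2 to 0.8.

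Formulas for a yes/no item:
- Variance explained: R² = p(1−p)d² / (1 + p(1−p)d²).
- Equivalent extra admissions: 1/(1−R²) − 1, which equals p(1−p)d².
- Narrowing of the interval: 1 − √(1−R²).

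Example, p = 0.5 and d = 0.8: p(1−p)d² = 0.25 × 0.64 = 0.16. So R² = 0.16/1.16 = 13.8%, extra admissions = 16%, and narrowing = 1 − √0.862 = 7.2%.

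| d | R², p = 0.4 | R², p = 0.5 | R², p = 0.7 | Extra admissions | Interval narrower by |
|---|---|---|---|---|---|
| 0.2 | 1.0% | 1.0% | 0.8% | 0.8-1.0% | 0.4-0.5% |
| 0.3 | 2.1% | 2.2% | 1.9% | 1.9-2.25% | 0.9-1.1% |
| 0.5 | 5.7% | 5.9% | 5.0% | 5.25-6.25% | 2.5-3.0% |
| 0.8 | 13.3% | 13.8% | 11.8% | 13.4-16.0% | 6.1-7.2% |

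**These are upper values, for two reasons.**
- R² here is marginal. Diagnosis is already in the model, and its categories (psychosis, mania, severe depression) may overlap with sleep complaints.
- The item acts on variance between admissions only. Night-to-night variance also enters the standard error and is untouched. If, for illustration, half the variance of an admission's observed mean is night-to-night noise, 13.8% falls to 6.9% and 0.8% to 0.4%.

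**Chance imbalance.** With n admissions per arm, treated as independent, the SE of the shift in an unadjusted contrast is d√(2p(1−p)/n). Assume n = 200 and p = 0.5. Then √(0.5/200) = 0.05, so two standard errors are 0.1d, or 0.02, 0.03, 0.05 and 0.08 SD for d = 0.2, 0.3, 0.5 and 0.8.

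**The case against.** The strongest reply is that nothing here is an error. Using one prespecified covariate set for all secondary outcomes is accepted practice, and leaving out a prognostic covariate does not by itself bias a randomised comparison. Both points stand, and they limit this to an improvement in the sleep models. The gain may also be negligible if the item is coarse or nearly every patient has it. At a prevalence of 0.9 and d = 0.2, for example, the interval narrows by only about 0.2%.

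A second reply concerns timing. The item describes a period before admission, but the SAP does not say when it is documented. Patients are randomised before any psychiatric assessment at the unit and the trial is unblinded, so an entry could be written by staff who know the ward. This also stands, and the fix has to guard against it.

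A reader might go further and infer any of three stronger points, which the SAP does not support:
- **That the key effect modifier has been missed.** Nothing in the SAP ranks prior sleep above other modifiers. Section 1.3.2 singles out diagnostic subgroups, and the wording of section 3.3.3 does not strictly close the list. Such a test would also be weak. If the main effect has 80% power, an interaction of the same size has power Φ(2.80√(p(1−p)) − 1.96), which is 29% at p = 0.5 and 13% at p = 0.9.
- **That the mediation analysis is confounded by this omission.** Section 5.4 plans to ask whether "improvement in sleep variables and intra-individual variability in sleep variables mediate the effect", but leaves this to later papers and names no confounder set. Section 1.1 says exploratory analyses are not detailed. The SAP has not excluded prior sleep from those models.
- **That the exclusions after randomisation in section 3.2.2 make the sleep contrasts biased through prior sleep.** They do mean that balance in the analysed set is not guaranteed, but nothing in the SAP shows that exclusion depends on prior sleep.

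**Conclusion.** The point holds as a modest improvement to secondary analyses. A recorded item in the same domain as the outcome has no stated use beyond the baseline table, while the five sleep models adjust for variables selected for a different outcome and have no listed pre-allocation radar value to adjust for.

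The direction of the benefit is clear if the item predicts ward sleep at all, but its size is not known. Under the assumed ranges it explains about 1-14% of between-admission variance, or roughly 0.4-7% of interval width for a yes/no item, with the true gain probably lower for the two reasons given above. The primary analysis of length of stay is unaffected. Subgroup and mediation uses of the item are optional exploratory ideas and not required changes.

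**What to change.** Before the statistician is unblinded, amend section 5.2.1 so that sleep problems in the previous month enter as a fixed covariate in the models for total sleep time, sleep onset latency, number of awakenings, wake after sleep onset and sleep efficiency. In the same sentence state:
- how the item is coded;
- that it is the value belonging to the admission analysed and rests on information about the period before that admission, not on observations made on the allocated ward;
- that unrecorded values form their own category, so that no admission is dropped. This coding is suitable for these randomised comparisons. It should not be carried over without thought to mediation models, where it could leave residual confounding.

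If the sponsor prefers not to adjust, a sentence saying why would suffice.

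The cost is wording and one or two degrees of freedom per model. The item is already planned for collection, and section 3.4.2 already provides for a published amendment on model decisions taken before unblinding.
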